5.2 SELECTION OF INSTRUMENTS

Data will be collected via medical record reviews and four PRO surveys: (Short Form [SF] Post-HCT Financial Assessment (Appendix B), Caregiver Quality of Life – Adapted Patient Survey (Appendix C), EORTC QLQ-C30 (Appendix D), and FACT-BMT (Appendix E). Medical record review will include sociodemographic information, diagnoses, recurrence, surgical procedures, cardiac events, and mortality. Patient survey data will include measures of the chosen PROs. All data will be entered into a password-protected RedCap database, with hard copies stored in locked file cabinets.

5.3 DESCRIPTION OF INTERVENTION

Shared Care involves four specific strategies to allow patients to be followed locally after HCT, where clinic and laboratory visits are equally shared between the local oncologist and primary HCT team. The challenges of delivering complex care will be met by addressing communication and knowledge gaps within each stakeholder group (transplant physician, local oncologist and patients/caregivers). As such, we have broken down the Shared Care intervention into four targeted components:

1. Formal Care Coordination Plan (CCP): A comprehensive online document created pre-HCT that will clearly define responsibilities of patients and their two teams of providers. This will be freely available for review by all three groups (Appendix F).
2. Patient Engagement and Education: The DFCI HCT program has numerous resources for patient education, covering nutrition, medication, and infection prevention. This includes the *Stem Cell Education: An Information Guide for Patients and Caregivers*, access to an online portal (sctpatiented.dana-farber.org – password *dfci*), and a transplant-specific CancerConnect community. Both Shared Care patients and Usual Care patients will receive all of these materials; Shared Care patients will also have specific pieces of education “pushed” to them through the ACT.md portal (Appendix G).
3. Local Oncologist Engagement and Education: Shared Care local oncologists will attend a three-day conference at DFCI’s HCT center before patient enrollment starts, aimed to address knowledge gaps and to educate them in management of HCT complications. For draft curriculum see Appendix H. There will also be yearly follow-up education at Dana-Farber which will feature review of post-HCT clinical scenarios and clear protocols for reaching out to the primary HCT team. Additionally, [name] and [name] will visit each of the local sites annually to discuss the study and answer any transplant-related questions.
4. Patient/Local Oncologist/Transplant Oncologist Web Portal: A patient-facing centralized web platform (ACT.md) will ensure timely communication with the two teams of providers, patients, and their families. The web portal will also be available for patients to share with emergency providers that they see locally (Appendix I).

5.4 DATA COLLECTION

A detailed Multi-Center Data and Safety Monitoring Plan Template (DSMP) is available in the Appendices (Appendix G).

Patient-Reported Outcomes: In a recent study (17-088) a modified Delphi technique was used to determine the optimal PROs and collection methods to measure patient quality of life after

Version 8 , 11/16/2020

transplant. Per the results of the study, patients will be asked to fill out the (SF) Post-HCT Financial Assessment (Appendix B), Caregiver Quality of Life – Adapted Patient Survey (Appendix C), EORTC QLQ-C30 (Appendix D), and FACT-BMT (Appendix E). The participants deemed that four surveys in one sitting is appropriate, since each of the surveys takes approximately 5 minutes to complete (for a total of 20 minutes to take all four surveys). All patients will be asked to complete PROs at DFCI visits close to 100 days and 180 days post-transplant. These surveys will be administered and collected by the research assistant.

HCT-Related Outcomes: We have chosen 100-day non-relapse mortality (NRM), as this is a standard measure for much of the clinical trial literature surrounding upfront interventions in HCT. We will also measure overall survival (OS) and GVHD symptoms. However, 100-day NRM is more directly applicable because it will be assessed during the critical time of the Shared Care intervention, which lasts 180 days. Transplant data management is unique in that all U.S. transplant centers are required to submit outcomes data for each allogeneic transplant they perform to the national Stem Cell Therapeutic Outcomes Database. To ensure all data are entered in a timely manner, the DFCI team will perform data quality review quarterly, and follow up on any delayed data entry for each patient enrolled.

5.5 DESCRIPTION OF STUDY PROCESS

This study of the effectiveness of the Shared Care method will be conducted with a randomized control trial comparing Shared Care and Usual Care. There will be 324 participants. Please see the protocol schema for the study time line. To review:

[figure not shown]
Pre-Transplant:

1. Recruit participants. Patient sign informed consent on day of overall HCT consent.
2. Patients randomized to one of two arms of the study.

Transplant:

Month 1: Patients admitted to DFCI or BWH for transplant. Receive stem cells.

1. Patients receiving full intensity allogeneic HCT will remain at the hospital for approximately 30 days.

Version 8 , 11/16/2020

2. Patients receiving a reduced intensity chemotherapy (RIC) HCT will be discharged approximately 1-2 days post-transplant. However, they will remain in Boston to attend frequent clinic visits until engraftment (10-12 days post-transplant).

Post-HCT: Full Intensity

Start of Shared Care: Patients will be discharged from hospital. Usual Care patients return to DFCI for all scheduled appointments through 180 days. Shared Care patients adhere to the following schedule:

1. For the first 90 days post-transplant, patients will alternate between local oncologist and DFCI for weekly visits.
2. From 90 to 180 days post-transplant, patients will alternate between local and DFCI every 2-3 weeks.

Post-HCT: Reduced-Intensity

Start of Shared Care: After evidence of engraftment at follow-up DFCI patient visits (ANC >500). Usual Care patients return to DFCI for all scheduled appointments through 180 days. Shared Care patients adhere to the following schedule:

1. For the first 90 days post-transplant, patients will alternate between local oncologist and DFCI for weekly visits.
2. From 90 to 180 days post-transplant, patients will alternate between local and DFCI every 2-3 weeks.

For patients who have not already established care with their designated local oncology team, a visit will be scheduled with that provider before HCT admission. An example of a Full Allo Shared Care patient's potential schedule is provided in Appendix K.

Premature termination of Shared Care:

Patients who relapse or require a second transplant will remain on protocol for QOL assessment but will no longer share care as part of the protocol.

5.51 Instrument Administration

In addition to the standard data collection that is required for all patients who undergo HCT in the United States (CIBMTR)—including NRM and overall survival (OS)—all patients will be asked to complete PROs at 100 days and 180 days post-transplant, including any patients that prematurely terminate Shared Care for any reason. This was determined based on recommendations made by the modified Delphi panel of patients from a previous study (17-088). PROs will focus on assessing physical, social, and emotional wellbeing.

Version 8 , 11/16/2020

To understand the care that is received by individuals who choose not to be randomized, for those who consent, the study will track in parallel fashion their HCT-related outcomes and PROs. This will provide a non-randomized observational cohort which will be a second source of analysis and will also allow us to determine if there is a participation bias for those randomized. Given exuberant non-randomized (NR) enrollment and since NR participants are not included in our main analysis, we will cap the number of participants enrolled in the non-randomized arm at 1 patient per month. This will further lessen the burden of data collection with our limited resources and will allow us to better utilize the time of our research assistant involved in data collection. Patients declining randomization will receive usual care following HCT at Dana-Farber.

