6.1 GENERAL DESCRIPTION AND CHARACTERISTICS OF DFCI HCT PATIENT POPULATION

Estimated study population characteristics are presented in Table 3, which are derived from our recent survey of patients at 180 days after HCT (in the table, autologous patients are excluded).^{4,11,12} More detail about PROs, handling of missing data, and heterogeneity of effects are detailed below.

Table 2. Shared Care Participating Sites and Number of Allogeneic HCT Patients in 2014 and 2015; Estimates for Accrual Per Year			
Proposed Shared Care Sites	State	Mean DFCI Allo HCT 2014 & 2015	If 80% agree to RCT/year
Stamford Hospital	CT	27	21
Dartmouth-Hitchcock	NH/VT	25	20
New York Oncology Hematology	NY	26	20
New England Cancer Specialists	S. ME	17	14
Eastern Maine Medical Center	N. ME	17	14
DFCI CCC/Satellites	MA	25	20
Total		136	108

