approaches to handling missing data from dropouts. First, to assure PRO scores for non-responders are missing at random, we will perform a sensitivity analysis comparing the patient, HCT characteristics, and clinical outcomes between responders and non-responders. Second, we will perform multiple imputation on the outcome variable (including all independent variables) and compare the result without multiple imputation (i.e., inclusion of responding patients only). More importantly, with voluntary patient consent to participate in the study and proactive collection of survey data by the research team, we anticipate that the non-compliance rate will be minimal (<5%). Moreover, we anticipate that there will be no missing independent variables in all HCT patient-related data as this data must be reported to the CIBMTR database by the DFCI/BWH HCT center. Finally, to assure the robustness of our results, we will compare the FACT-BMT scores of the randomized Usual Care cohort with the non-randomized usual care cohort.

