DSMB meetings close with an executive session to summarize and evaluate the overall meeting, finalize recommendations, and plan the next meeting. The Principal Investigator ([name]) and the Study Biostatistician ([name]) will be available as needed for each meeting of the DSMB and be responsible for disseminating and implementing any concerns to PCORI, the SCIG, the SC-PAP, and other Stakeholders.

The Participating Sites and the Lead Institution will maintain communication regarding a patient's care via email, telephone, pager, and a HIPAA-compliant web app, ACT.md. ACT.md will be used as a communication platform for patients, local oncologists, and transplant oncologists during Shared Care

Monitoring Reports

The DF/HCC Sponsor will review all monitoring reports to ensure protocol compliance. The DF/HCC Sponsor may increase the monitoring activities at Participating Institutions that are unable to comply with the protocol, DF/HCC Sponsor requirements or federal and local regulations.

Accrual Monitoring

All accrual will take place at the Lead Institution, DFCI. We anticipate a total of 324 randomized patients, as well as 84 non-randomized patients who will receive all their care at the Lead Institution. Though, no accrual will take place at any Participating Site, we anticipate the following number of patients per year to be referred from or live near each Participating Site:

Lifespan Cancer Institute: 21 participants

Dartmouth-Hitchcock: 20 participants

New York Oncology and Hematology: 20 participants

Version 8 , 11/16/2020

New England Cancer Specialists: 14 participants

Eastern Maine Medical Center: 14 participants

DFCI Community Cancer Care: 20 participants

AUDITING: QUALITY ASSURANCE

Auditing is a method of Quality Assurance and involves the systematic and independent examination of all trial related activities and documents. Audits determine if evaluated activities were appropriately conducted and whether data was generated, recorded and analyzed, and accurately reported per the protocol, applicable Standard Operating Procedures (SOPs), and the Code of Federal Regulations (CFR).

DF/HCC Internal Audits

All Participating Institutions are subject to audit by the DF/HCC Office of Data Quality (ODQ). Typically, approximately 3-4 participants would be audited at the site over a 2 day period. If violations which impact participant safety or the integrity of the study are found, more participant records may be audited.

Audit Notifications

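### The mid-study cap on non-randomized entry makes calendar period a likely confounder of the participation-bias check, and the planned comparison is too imprecise to assure robustness

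*Combined protocol and SAP*

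**What the plan says.** Section 5.51 (Instrument Administration) sets up a parallel cohort of patients who decline randomization but agree to follow-up. It serves as an additional analysis and, in the plan's words, "will also allow us to determine if there is a participation bias for those randomized". The same paragraph then limits entry. It opens with a reason: "Given exuberant non-randomized (NR) enrollment and since NR participants are not included in our main analysis". The limit itself reads: "we will cap the number of participants enrolled in the non-randomized arm at 1 patient per month". Research assistant workload is the other reason given.

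The cohort has two later uses. Section 6.3 (Handling of Missing Data) says "to assure the robustness of our results, we will compare the FACT-BMT scores of the randomized Usual Care cohort"; the comparator is the cohort of decliners under usual care. Section 6.4 (Non-relapse Mortality) plans a sensitivity analysis of baseline characteristics and clinical outcomes, comparing the non-randomized group with each randomized arm. Neither section mentions the cap or enrollment period.

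The Data and Safety Monitoring Plan, under Accrual Monitoring, states "We anticipate a total of 324 randomized patients". For decliners it adds: "as well as 84 non-randomized patients who will receive all their care at the Lead Institution". The documents do not give the date the cap began, the number of non-randomized patients enrolled by then, or a rule for which consenting decliner fills the monthly place.

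**The concern.** A check for participation bias asks whether people who accept randomization differ from people who decline it. For that, the two groups should differ in acceptance and, as far as possible, in nothing else that affects outcome. The cap slows entry to one group only, and does so partway through. The non-randomized cohort then draws more of its patients from early in the study than the randomized arms do. If FACT-BMT scores or clinical outcomes shift over time, the comparison reflects that shift as well as any effect of declining.

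The cohort will also be smaller than uncapped entry would have made it, while section 6.3 still treats the comparison as assurance. At stake is a misreading of a supportive analysis: a similar mean taken as proof of no participation bias, or a different mean taken as proof of it.

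**Working it through.** **Inputs.** From Table 2 (section 6.1): 136 eligible transplants per year ("Mean DFCI Allo HCT 2014 & 2015") and 108 randomized per year ("If 80% agree to RCT/year"). From section 6.2: 80% alive and 70% responding at day 180; 180 scores in all, so 90 per arm; SD 20; a 10-point difference as the smaller effect considered. From section 5.51: a cap of 12 per year.

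**The plan's power figure.** For the Wilcoxon test with 90 per arm, power = Φ(√(3/π) × 10 / (20√(2/90)) − 1.96) = 0.906, which matches the stated 90%. SD 20 is therefore used as the per-patient SD.

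**Where 84 comes from.** The plan gives no derivation. Expected decliners are 136 − 108 = 28 per year and accrual lasts 324/108 = 3 years, so 28 × 3 = 84, an exact match. The table rows sum to 137 and 109 rather than 136 and 108, but the difference is still 28. So 84 corresponds to every expected decliner, 2.33 per month, with no cap. The cap admits 12 of 28 per year (43%).

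**Cohort size and balance.** The cap's start is unknown, so it is assumed to fall at month 12, 18 or 24 of a 36-month accrual, with decliners entering at the planned 2.33 per month beforehand and even randomized accrual throughout.

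| Cap starts | Before cap | After cap | Total | Non-randomized, share before cap | Randomized, share before cap | Gap |
|---|---|---|---|---|---|---|
| Month 12 | 28 | 24 | 52 | 54% | 33% | 0.21 |
| Month 18 | 42 | 18 | 60 | 70% | 50% | 0.20 |
| Month 24 | 56 | 12 | 68 | 82% | 67% | 0.16 |

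The last column is the fraction of any drift that enters the unstratified comparison, if survival and response are the same in both periods. If mean FACT-BMT differed by 10 points before and after the cap, the comparison would be shifted by about 1.6 to 2.1 points with no participation bias at all.

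If early entry ran above plan, the imbalance is larger. Reaching 84 in 36 months needs 60, 66 or 72 patients before the cap (5.0, 3.7 or 3.0 per month). The shares before the cap are then 71%, 79% and 86%, and the gaps 0.38, 0.29 and 0.19.

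**Precision.** Scores = 0.80 × 0.70 × N = 0.56N. SE = 20√(1/90 + 1/(0.56N)). Half-width = 1.96 × SE. Power for 10 points = Φ(10/SE − 1.96), two-sided 0.05.

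| N | Scores | SE | 95% half-width | Power, 10 points |
|---|---|---|---|---|
| 84 | 47.0 | 3.60 | 7.1 | 79% |
| 68 | 38.1 | 3.87 | 7.6 | 73% |
| 60 | 33.6 | 4.04 | 7.9 | 70% |
| 52 | 29.1 | 4.26 | 8.4 | 65% |

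**Cost of comparing within period.** With patients split as in the first table and the two period differences combined by inverse-variance weights, SE = 20/√Σ[ab/(a+b)], where a and b are the non-randomized and Usual Care scores in each period. For the cap at month 12 the terms are 15.68 × 30/45.68 = 10.30 and 13.44 × 60/73.44 = 10.98, so SE = 20/√21.28 = 4.34 and the half-width is 8.5 against 8.4 unstratified. For months 18 and 24 it is 8.1 against 7.9, and 7.7 against 7.6.

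**The case against.** The strongest reply is that non-randomized patients are outside the main analysis. That stands: the randomized FACT-BMT comparison and the intention-to-treat NRM comparison are untouched. It also stands that calendar imbalance does harm only if outcomes drift, that the documents show no drift, and that the baseline comparison in section 6.4 would reveal measured differences. It would not reveal a change in care or scoring over time.

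A reader might go further in three ways that the documents do not support.

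- **That 84 cannot be reached.** A cap in force from the first month would allow 36 in 36 months or 48 in 48 months. But section 5.51 presents the cap as a response to high enrollment already seen. Without its start date and the count at that date, 84 may have been close or even passed. The monitoring plan also calls it an anticipated number. For the same reason, power worked out on 36 or 48 patients does not describe this cohort.
- **That the capped patients are hand-picked.** No section says the team chooses among decliners. Workload is given as a reason to limit the number, and taking the first consenting decliner each month fits the wording equally well. The rule is simply not stated.
- **That the participation-bias question will be answered wrongly.** The comparison is imprecise and exposed to drift. That is not the same as being shown to be biased.

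**Conclusion.** The point holds as a limited one about a supportive analysis. The cap probably leaves the non-randomized cohort weighted to the earlier period, and the comparisons in sections 6.3 and 6.4 take no account of it. On planned rates, 16 to 21% of any drift between periods would pass into the comparison, and more if early enrollment exceeded plan. The 84 rests on uncapped entry and has not been reconciled with the cap.

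Precision limits the claim whatever the final count. At 84 patients the interval is about ±7.1 points; at 52 to 68 it is ±7.6 to 8.4, with 65 to 73% power for a gap of 10 points, the difference for which the trial itself claims 90% power. A non-significant result would leave sizeable differences open and cannot assure robustness.

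These figures assume a 36-month accrual, a cap starting between months 12 and 24, entry at the planned decliner rate until then, even randomized accrual, and the randomized cohort's survival, response and SD applied to decliners.

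**What to change.** Keep the cap and make four changes.

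1. In sections 6.3 and 6.4, compare non-randomized with randomized patients from the same enrollment period, stratifying or adjusting for before and after the cap.
2. In section 6.3, report the FACT-BMT difference with its 95% CI, and replace the assurance wording with a statement of which differences the interval excludes.
3. In section 5.51, give the date the cap began and the non-randomized count at that date, and state that the first consenting decliner of each calendar month is enrolled.
4. In the monitoring plan, restate 84 as the number enrolled before the cap plus one per month.

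The cost is a few sentences and no extra patients or staff. The interval widens by about 0.1 point of half-width under the assumptions above.

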5.52 Intervention Administration

Along with care at DFCI, patients randomized to Shared Care will receive half of their care at one of six community practice sites (Stamford Hospital, Dartmouth-Hitchcock, New York Oncology Hematology, New England Cancer Specialists, Eastern Maine Medical Center, and DFCI Community Cancer Care/Dana-Farber Satellites).

Each local site will be responsible for obtaining local IRB approval after OHRS approval at DFCI (except for DFCI Community Cancer Care/Dana-Farber Satellites), and all Shared Care Investigator Group (SCIG) members (DFCI and local) will require receipt of education in the protection of human research participants (CITI training). Site investigators and clinicians will also receive HCT training in post-HCT care in Boston, and training in the use of the selected HIPAA-compliant web app, ACT.md. ACT.md will be used as a communication platform for patients, local oncologists, and transplant oncologists during Shared Care. Clinical outcomes will be collected in government-mandated systems already in place for HCT patients at DFCI and maintained by the Dana-Farber Department of Research Computing. PROs during the first 180 days will be collected by the Research Assistant when patients are at Dana-Farber.

GVHD is a potential outcome of an allogeneic HCT transplant. It is a condition where the new cells attack the recipient's tissues, such as the skin and gastrointestinal tract, and specialized anti-rejection medications must be managed closely. The GVHD-related tasks segment of ACT.md will be very detailed because local oncologists will be most unfamiliar with looking for and treating GVHD. There will be a flowsheet integrated in the system that will document the level of GVHD if any.¹⁸

Shared Care will start on the first clinic visit after stem cell engraftment (reduced intensity transplant), or after hospital discharge (myeloablative transplant). Importantly, we will aim to have the first post-engraftment or post-discharge visit for patients randomized to Shared Care to occur locally even if patients are experiencing post-transplant complications. Transplant teams will provide a "warm pass-off" to the local team before this visit, send a discharge summary of the inpatient stay, and make sure that the online comprehensive care plan is reviewed by all parties.

Version 8 , 11/16/2020

